#### Upper and lower dose limits for whole breast PTV

Lower dose limit	Prescription dose	Upper dose limit
	Use START ref	
>95% of the volume should receive 95% of the prescribed dose	point for tangents, seek QA advice for inverse- planned	<5% of the volume should receive ≥105% <2% of the volume should receive ≥107% global max <110% of the prescribed dose

Table 2: upper and lower dose limits for whole breast PTV

#### 12.1 Dose Constraints for Organs at Risk (OAR)

The dose constraints for whole breast radiotherapy using tangential field arrangements are listed below. If non-tangential fields are used, e.g. inverse planned IMRT for patients with pectus excavatum or very medial tumour bed, then the planner must seek advice of the QA team. These constraints do not take into account the tumour bed boost dose. Although maximum dose constraints are stated for the heart, the planner should aim to keep any dose to the heart as low as possible.

# **Control group**

- The volume of ipsilateral lung receiving 12.0 Gy should be less than 15%
- The volume of heart receiving 2.0 Gy and 10.0 Gy should be less than 30% and 5% respectively.

## Test group 1 and 2

- The volume of ipsilateral lung receiving 8.0 Gy should be less than 15%
- The volume of heart receiving 1.5 Gy and 7.0 Gy should be less than 30% and 5% respectively.

Dose per fraction (Gy)	Keep 30 % of dose to < 15 % of ipsilateral lung volume	Keep 25 % of dose to < 5 % of heart volume	Keep 5 % of dose to < 30 % of heart volume		
2.67	12.0 Gy	10.0 Gy	2.0 Gy		
5.2/5.4	8.0 Gy	7.0 Gy	1.5 Gy		

#### 12.2 Bolus

Centres should specify prior to randomisation whether or not post-mastectomy (+/-reconstruction) bolus is to be applied, and if so, whether it is to be applied a) to part (e.g. the scar area) or all of the chest wall, b) for all or a specified number of fractions and c) thickness of bolus used for a given photon energy. Either composite plans, or plans with and without bolus are to be sent to the QA team for DVH assessment. Bolus is not applied after breast conservation surgery.

#### 12.3 Beam Energy

Beam energies for treatment as for local practice, usually 6 MV, but a mixture of energies e.g. 6 MV and 15 MV can be used for larger patients.

#### 12.4 Tumour bed radiotherapy

The tumour bed boost treatments can be either delivered by electron or photon beams. Either 10.0 Gy in 5 fractions or 16.0 Gy in 8 fractions is prescribed to the 100% isodose. Centres should aim to contour the boost volume and, where possible, produce dose distributions on their planning system and send boost plans to the QA team. If clinical mark up is used for planning, CT information must be used to guide localisation of the tumour bed, for example, using the information on clip position and the use of surface rendered views (if these can be produced from the planning system). Details on minimum requirements for tumour bed boost radiotherapy can be found in the planning pack.

#### 13. TREATMENT SCHEDULING AND GAPS

Treatment can start on any day of the week.

A gap of up to 3 days is acceptable in the event of machine service or breakdown. This is preferable to transferring the patient to a machine on which daily verification imaging is not available. If the treatment machine is unavailable for more than 3 days, please contact the QA team.

#### 14. RADIOTHERAPY VERIFICATION

#### 14.1 Treatment Set-up Verification – Breast and Chest Wall

Verification is carried out using electronic portal imaging of the treatment beam. This can be either MV or kV.

**Control group:** Treatment verification is required for at least three fractions in the first week of treatment to determine, and correct for any systematic error\*. Correction is carried out following local practice as long as this has been approved by the QA team. This correction is applied on fraction 4, with imaging to confirm the move. A suitable tolerance for the check of the correction is 5 mm. Verification is then once weekly throughout the remaining whole breast field treatment with a tolerance of 5 mm.

\*All systematic errors should be corrected if possible, and this is recommended, but if a centre wishes to use a correction tolerance on systematic error it should not be greater than 5 mm, and preferable not more than 3 mm and reported to the QA team

**Test group 1 and 2**: Verification imaging and correction are required for each fraction. Set up error is corrected on each fraction prior to treatment, with a further image taken to confirm the correction. A tolerance of 5 mm is suitable for the check of the correction.

#### 14.2 Treatment Set-up Verification - boost

#### **Electron Boost**

The electron boost set up is verified daily by visual matching to marks on the skin and checks on the gantry and collimator angles required for matching.

#### **Photon Boost**

An off-line verification protocol is recommended. This consists of imaging on the first two fractions. The calculation of any systematic error from this data is then carried out and the correction for the systematic error is applied on fraction three. A check image is recommended prior to treatment on fraction three. A suitable tolerance for the check is 5mm. This protocol is appropriate for a PTV margin of 10 mm.

Where the boost fractionation is 16.0Gy in 8 fractions, centres may wish to image on/around fraction 6 as a further check; again a suitable tolerance is 5 mm.

Where the need for more complex treatment planning (e.g. inverse planning or tomotherapy) requires a verification method not described here, centres are requested to discuss this on an individual basis with the QA Team. Similarly, if a centre wishes to use a tighter PTV margin with a more stringent verification protocol, this should be discussed with the QA Team.

#### 14.3 In-vivo Dosimetry

In line with current UK guidelines, all FAST-Forward patients should have in-vivo dosimetry within the first week of treatment. This may be performed using diodes or thermo-luminescent dosimetry (TLD). Other methods may be appropriate for individual centres and should be discussed with the QA team.

#### 15. RADIOTHERAPY QUALITY ASSURANCE

A comprehensive quality assurance programme is planned for all centres involved with FAST-Forward (see Appendix 3).

#### 16. SERIOUS ADVERSE EVENT REPORTING

#### 16.1 Definitions

Adverse Event (AE): any untoward medical occurrence in a patient or clinical trial subject administered a research procedure; events do not necessarily have a causal relationship with the procedure.

**Related Adverse Event:** an adverse event assessed by the Principal Investigator or Chief Investigator as reasonably likely to be related to the administration of a research procedure.

#### **Serious Adverse Event (SAE):** an untoward occurrence that:

- 1. results in death
- 2. is life-threatening
- 3. requires hospitalisation or prolongation of existing hospitalisation
- 4. results in persistent or significant disability or incapacity
- 5. consists of a congenital anomaly or birth defect
- 6. is otherwise considered medically significant by the Principal Investigator

N.B. Progressive disease and death due to disease are not considered SAE's but should be reported on the relevant forms.

**Related Unexpected Serious Adverse Events:** an adverse event that meets the definition of serious and is assessed by the CI or nominative representative as:

- "Related" that is, it resulted from administration from the research procedure, and
- "Unexpected" that is, the type of event is not listed in the section below as an expected occurrence

#### 16.2 Reporting Serious Adverse Events

All SAEs should be reported within 24 hours of the investigator becoming aware of the event, by completing the FAST-Forward SAE form and faxing it to the FAST-Forward Trial Manager, Clinical Trials and Statistics Unit, [name] (Monday – Friday 09.00-17.00). The SAE form must be completed, signed and dated by the Principal

Investigator or nominated person identified on the centre delegation log. ICR-CTSU will send a fax back to the centre to acknowledge receipt of the SAE.

Any relevant follow up information, including final resolution of the event, should be completed on the relevant part of the original SAE form and faxed to the ICR-CTSU within 15 days of the local investigator becoming aware of this information. The Chief Investigator (or a nominated representative) will review all SAEs to assess relatedness and expectedness.

The centre SAE log should be completed and the SAE form filed in the Site Investigator File.

SAEs will be collected during the patient's radiotherapy and for three months following treatment.

#### 16.3 Reporting Related and Unexpected SAEs

If an SAE is defined as related and unexpected by the Chief Investigator, ICR-CTSU will report the SAE to the main REC within 15 days from the date the ICR-CTSU became aware of the event. Any subsequent reporting will be carried out as appropriate.

N.B. Patients showing unexpectedly severe late normal tissue responses will be identified on the Follow-up Forms and are not reported as SAEs. These late-occurring reactions include unexpectedly severe late subcutaneous fibrosis, ischaemic heart disease (after both right- and left-sided radiotherapy), rib fracture and symptomatic lung fibrosis.

#### 17. STATISTICAL CONSIDERATIONS

#### 17.1 Choice of Principal Outcomes

Primary outcome is ipsilateral local tumour control, since this is the justification for treatment. Other endpoints include normal tissue effects and quality of life. It is intended that each endpoint will be analysed separately. If there is discordance between the endpoints in terms of treatment outcome this will allow discussion of clinical trade-offs.

#### 17.2 Methods of Analysis

Survival analysis methods (i.e. Kaplan-Meier analysis and Cox proportional hazards regression) will be used to compare rates of local recurrence between allocated treatments for all randomised patients (i.e. intention to treat). Normal tissue effects will be analysed using methodology developed for the START Trials; i.e. survival analyses of time to occurrence of moderate or marked effects, as appropriate. Analysis of the QL data will follow algorithms developed for the QL forms (i.e. calculation of standardised sub-scale scores), and will compare treatment groups at individual time points, as well as longitudinal changes from baseline. A generalised linear modelling approach will be used to describe the longitudinal QL data, taking into account important prognostic factors such as age, stage of disease, treatment received and other socio-demographic and clinical characteristics. Appropriate adjustments will be made for multiple comparisons in the analysis of the QL data by adopting a more stringent cut-off for statistical significance.

The sample size calculations have been based on survival analysis methods. The 5-year figure has been used as the clinically relevant time point and assumes that recurrences before and after five years will be included in the analysis accordingly (i.e. patients will be followed from randomisation until it becomes impractical to do so further, and patients will only be censored in the analysis upon death or if lost to follow-up). Analyses will incorporate the time to an event as well as the occurrence of that event.

As this is a non-inferiority trial if there is high non-compliance with the test treatment groups then an analysis of only those compliant with the protocol will also be conducted.

The incidence of uncommon serious complications will be monitored.

Analyses of local tumour recurrence and of normal tissue effects adjusting for adjuvant therapy (chemotherapy, hormonal therapy) will be performed. Analyses of normal tissue effects will also be adjusted for breast size and surgical deficit.

Analyses will estimate the size of treatment effect with a confidence interval for the estimated difference between schedules. Information will be provided on both the absolute and relative treatment effect. Each Test group will be compared with the

Control group and treatment effects estimated separately. The inclusion of two test dose levels (Test 1 & 2) allows minor adjustment, for example by interpolation, between test dose levels to identify the fraction size most closely resembling the control schedule in terms of late change in breast/chest wall appearance and other adverse effects. The primary comparison is the rate of local tumour control at this 5-fraction dose level compared to the 15-fraction control. Since local relapse rates are so low, and no measurable difference in local relapse between the two test schedules is expected, interim analyses will also combine the test schedules for comparison with the control for the primary endpoint.

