# Patient eligible for FAST Forward and consents to participate

Baseline Quality of Life questionnaires – **prior to randomisation**Baseline photographs of breast/chest wall following surgery – **prior to radiotherapy**Blood sample collection/family history questionnaire – **at any time** 

\*16 Gy or 10 Gy in 2 Gy fractions sequential electron or photon boost to the tumour bed is allowed in all 3 treatment arms (boost decision to be declared before randomisation for each individual patient)

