## 1) Normal tissue effects and body image

The proportion of patients suffering breast, arm and shoulder symptoms together with specific post-RT symptoms will be assessed at baseline, 3 and 6 months, 1, 2, 5 and 10 years. Relevant symptoms from the breast cancer module (EORTC BR23) and protocol-specific post RT symptoms, all scored as 'quite a bit' or 'very much' will be used as an indicator of adverse effects. Body Image concerns will be summarised for comparison between regimens, and where appropriate, individual items will also be compared.

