## **Timing of Assessments**

The emphasis is on the long-term assessment of different treatment policies. Evaluation points are designed to allow comparison with the START and IMPORT LOW and HIGH trial QL outcomes.

**Baseline Quality of Life:** All measures: EORTC QLQ-C30 and BR23, Protocol specific pre-RT items, Body Image Scale, EORTC Fatigue module and HADS.

A designated member of staff, trained in QL administration, will hand out questionnaires in the clinical centre. Patients will be asked to complete the questionnaires after a full explanation of the study and after giving informed consent but **before** the randomisation is known, to avoid the possibility of bias.

**Quality of Life Follow-up**: Results of the START trials indicated a rise in breast symptoms at the 6-month evaluation and more precision is needed in estimating these effects closer to

treatment. All QL measures (EORTC QLQ-C30 and BR23, Protocol specific post–RT breast symptoms, BIS, HADS and the EORTC Fatigue module) will therefore be mailed to patients from the FAST-Forward Trials Office at 3 and 6 months and 1, 2, 5, and 10 years.

Follow-up - general aspects of QL: administered by the trials office, will be made as follows: Due care will be taken to check the physical status of all patients prior to questionnaire mailing. This will be done through telephone contact with the hospital department and/or GP as appropriate. The follow-up questionnaires will be sent out by the FAST-Forward Trials Office requesting completion within the week. If the questionnaires have not been returned 2 weeks after having been sent out, a letter will be sent to the patients enclosing another booklet requesting completion and return in the usual way. The follow-up assessments will be sent out shortly after the patient attends the hospital for routine annual follow-up, thereby ensuring that information on the patient's health status is up to date. Where necessary, information about the patient's current well-being will be confirmed by email with a named person in the centre before sending a booklet.

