# **Statistical Analysis Plan**

The algorithms developed for use with the QL questionnaires will be used to measure the parameters of interest. Groups of patients will be compared at agreed time points and overall for differences in these parameters [10]. The treatment groups will be compared at the individual time points with appropriate adjustments being made for multiple comparisons. Normal tissue effects will also be analysed using methodology developed for the START Trials i.e. survival analyses of time to occurrence of moderate or marked effects (scored 'quite a bit' or 'very much'). Because of the longitudinal nature of the data, an analysis which takes into account the repeated measures is also needed. A generalised linear modelling approach will be adopted [11-13]. This will allow the appropriate error distribution to be used and will enable the analysis to take account of important factors such as age, stage of disease, treatment received and other socio-demographic and clinical characteristics.

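### The planned quality-of-life comparisons do not condition on the pre-randomisation baseline score, so precision that the collected data already offer is given up

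*Protocol*

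**What the plan says.** - **Contrasts.** Protocol section 17.2 has QL responses converted to standardised sub-scale scores and says that the analysis "will compare treatment groups at individual time points, as well as longitudinal changes from baseline".
- **Appendix 4, Statistical Analysis Plan.** "The treatment groups will be compared at the individual time points with appropriate adjustments being made for multiple comparisons". Multiplicity is the only adjustment attached to that comparison.
- **Longitudinal model.** Appendix 4 adds that "an analysis which takes into account the repeated measures is also needed" and adopts generalised linear modelling, so that the analysis can "take account of important factors such as age, stage of disease, treatment received and other socio-demographic and clinical characteristics". Section 17.2 describes the same model as "taking into account important prognostic factors such as age, stage of disease, treatment received and other socio-demographic and clinical characteristics". Both lists are introduced by 'such as'. Neither names the baseline QL score and neither excludes it.
- **Baseline data.** The trial schema (4.1) places the "Baseline Quality of Life questionnaires" before randomisation. Appendix 4, Timing of Assessments, lists for that visit: "All measures: EORTC QLQ-C30 and BR23, Protocol specific pre-RT items, Body Image Scale, EORTC Fatigue module and HADS". They are completed before the allocation is known.
- **Symptom outcome.** Appendix 4 dichotomises breast and post-radiotherapy symptoms at 'quite a bit' or 'very much', which "will be used as an indicator of adverse effects" at each visit.

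**The concern.** A patient's own baseline score is usually among the strongest predictors of the same score later. A comparison at a single time point ignores it. A change from baseline, read plainly, subtracts it with a coefficient fixed at 1. An analysis of covariance estimates that coefficient and, for continuous scores, has asymptotic variance no larger than either.

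QL carries the patient-reported side of the trade-off with local control (17.1 and Appendix 4), and it covers many sub-scales at a stricter significance level, so precision is worth having. Two parallel contrasts also leave it open which one governs if the groups happen to differ at baseline.

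**Working it through.** **Inputs.** From 17.3.3 and Appendix 4, Sample Size: 732 per group, 80% power, an 8% difference, a 5-year rate of 35%, two-sided alpha 0.025 and 10% attrition. The baseline to follow-up correlation rho is not in the protocol. It is an assumption here, shown from 0.3 to 0.7, with equal SD at both times.

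**Step 1: the protocol's own figure.** Take 35% against 27%, with mean 31%.

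n = [2.241·√(2·0.31·0.69) + 0.842·√(0.35·0.65 + 0.27·0.73)]² / 0.08² ≈ 634 to 635 per group.

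The continuity correction gives 659. Then 659/0.90 = 732.2, which agrees with the stated 732. This is a calculation for a binary prevalence without covariates. It supplies 659 evaluable per group for what follows.

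**Step 2: relative variances for a continuous score.** Variance of the group contrast, in units of the follow-up-only contrast:

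- follow-up score alone: 1
- change from baseline: 2 - 2·rho
- baseline-adjusted: 1 - rho²

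Relative to the adjusted analysis, the follow-up score has variance 1/(1 - rho²) and the change score 2(1 - rho)/(1 - rho²) = 2/(1 + rho).

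**Step 3: power.** The sum of normal quantiles is 2.241 + 0.842 = 3.083. The difference detectable with 80% power on the follow-up score is 3.083·√(2/659) = 0.170 SD. For that difference, power = Φ(3.083/√(relative variance) - 2.241).

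| Assumed rho | Variance vs adjusted: follow-up | Variance vs adjusted: change | Power: follow-up | Power: change | Power: adjusted |
|---|---|---|---|---|---|
| 0.3 | 1.10 | 1.54 | 80% | 64% | 84% |
| 0.5 | 1.33 | 1.33 | 80% | 80% | 91% |
| 0.7 | 1.96 | 1.18 | 80% | 96% | 98% |

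Example at rho 0.5: 3.083/√0.75 - 2.241 = 1.319, and Φ(1.319) = 0.906. The detectable difference falls from 0.170 to 0.170·√0.75 = 0.147 SD. Equivalently, 659·0.75 ≈ 494 evaluable per group would give the precision of 659 unadjusted. Below rho 0.5 the change score is less precise than ignoring baseline altogether. At rho 0.2 the adjusted analysis reaches 82%, only 2 points above the follow-up comparison.

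**Step 4: symptom prevalence.** The formulas in step 2 do not carry over to a binary outcome, so this was simulated. Settings: 3,000 trials per rho, 659 per group, 35% against 27%, a latent normal correlation rho, a four-level baseline item with assumed frequencies 50/30/14/6%, and a robust test of the risk difference with and without the baseline item. Power rises from about 82% to 84% at rho 0.3, from 82% to 87% at 0.5 and from 81% to 92% at 0.7. The correlation and the item frequencies are both assumptions.

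**The case against.** **The protocol does not say that baseline is left out.** A reader might infer that the plan rules out the baseline score. It does not. The covariate lists are open, a repeated-measures analysis is planned, and the exact covariate set is commonly settled in a separate analysis plan, which is not at hand. This stands for the longitudinal model, where the omission is only unclear. It carries less weight for the contrasts. The protocol chooses those itself, and Appendix 4 has its own analysis section, where the time-point comparison carries an adjustment for multiplicity and no other.

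**The change comparison may not be a plain change-score test.** The text names longitudinal changes without giving a model, so a coefficient of 1 is the plain reading and not a stated method. A clarifying sentence would settle this.

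**The scores are not raw.** A reader might describe the comparison as one of raw scores. The protocol specifies standardised sub-scale scores. What is absent is conditioning on baseline.

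**Not every item has a baseline twin.** Appendix 4 lists protocol-specific pre-radiotherapy items at baseline and post-radiotherapy items at follow-up, and some of the latter ask about change in appearance. The documents do not show that these are the same items. This stands, and limits the remedy to items asked on both occasions.

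**The sub-study is powered on prevalence, not on mean scores.** This also stands. The 0.17 SD difference is derived here and appears nowhere in the protocol. The prevalence gain is smaller and depends on more assumptions.

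**QL is secondary and partly descriptive.** Appendix 4 treats it as supporting data, and does not expect formal tests for sexual functioning or distress. That limits the weight of the point without removing it.

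**Conclusion.** The point holds as one of efficiency and clarity on a secondary endpoint. The stated QL contrasts do not condition on a baseline score collected before allocation, and nothing in the text commits the longitudinal model to using it.

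A reader might go on to infer that the QL comparisons are biased, that the sub-study is too small, or that the primary conclusion is at risk. The documents support none of these: randomisation keeps the comparisons unbiased, 732 per group reproduces without covariates, and the local control analysis is untouched. The time-to-occurrence analyses are outside this point.

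The size depends on a correlation that the protocol does not give, and on the baseline score in fact being left out. For scale scores, the gain over the time-point comparison is about 2 to 4 points of power at rho 0.2 to 0.3 and about 11 points at 0.5. The gain over the change score is about 20 points at rho 0.3 (84 - 64) and 2 points at 0.7 (98 - 96). For prevalence, the simulated gain is about 2, 5 and 11 points at latent rho 0.3, 0.5 and 0.7. At low correlation the benefit is therefore minor.

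**What to change.** In section 17.2 and in the Statistical Analysis Plan part of Appendix 4, state that:

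- between-group comparisons of QL scores, at each time point and in the longitudinal model, include the baseline score of the same scale as a covariate, or come from a repeated-measures model with a common baseline mean across groups;
- comparisons of the prevalence of 'quite a bit' or 'very much' adjust for the baseline item where the same item was asked at baseline, and are reported as an adjusted risk difference;
- unadjusted scores and changes from baseline are descriptive summaries.

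The cost is wording only, with no new data, visits or patients. The one addition is a rule for missing baseline scores, for example single mean imputation, which is acceptable for a pre-randomisation covariate.

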A gain in local tumour control due to shortening treatment time to 1 week is possible. Evidence based on retrospective studies for an influence of treatment time on local tumour control is conflicting with recent systematic reviews drawing different conclusions [11, 12]. Even without a gain in tumour control, accelerated radiotherapy is likely to be more convenient for patients, and may ease scheduling with other treatment modalities. A pilot study (N = 30) tested 30 Gy in 5 fractions of 6.0 Gy in 15 days to the whole breast in terms of acute adverse effects and late effects at 2 years [13]. In this series, 23/30 (77%) patients scored no change in post-operative breast appearance at 2 years, 7/30 (23%) scored mild change and none scored marked change. The acute skin reactions were mild, with no reaction more severe than grade 2 erythema, scored in 9/30 (27%) patients. If the results of the proposed randomised trial support a 5fraction schedule delivered in 1 week, these will transform international breast radiotherapy practices. In conclusion, it is fair to say that after decades of resistance to evaluating larger radiotherapy fraction sizes in breast cancer, expert opinion is responding to an accumulating body of evidence supporting the safety and effectiveness of this approach.

Against this background, a phase III randomised trial is described with the primary aim of testing local tumour control in women with early breast cancer following a 5-fraction schedule of adjuvant radiotherapy delivered in 1 week. Stratification by treatment centre and by local relapse risk will ensure balanced trial groups (high risk defined as patient age <50 and/or grade 3 tumour; low risk defined as age ≥50 and grade 1 or 2 tumour) [14].

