#### 7.2 Treatment allocation

Treatment allocation will be 1:1:1 and will use computer-generated random permuted blocks. Randomisation will be stratified by centre and risk group.

A fax will be sent to the randomising centre to confirm the trial number and treatment allocation.

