#### 17.3 Sample Size

#### **17.3.1. Main Trial**

The target sample size is 4000 patients, with numbers balanced equally in each randomised group. This provides 80% power (1-sided  $\alpha$  = 0.025 to allow for 1-sided hypothesis and multiple testing) to exclude an increase of 1.6% in the 5-year local relapse rate between each test group and the control, assuming a 5-year rate of 2% in the 40.05 Gy schedule (using START data and allowing for reduction in local relapse due to recent adoption of aromatase inhibitors and trastuzumab). As local relapse rates after radiotherapy are low, there is limited potential for reducing this even further when comparing different regimens in a trial. Therefore the aim is to test whether the local relapse rate in the test groups is at least as effective, and not more than 1.6% higher than in the control group. Since local relapse rates are so low, and no measurable difference in local relapse between the two test schedules is expected, interim analyses will also combine the test schedules for comparison with the control for the primary endpoint. This combined analysis will enable an excess of 1.3% in the 5-year local relapse rate of the test groups relative to the control to be excluded (80% power). As follow-up continues and more events accrue, the statistical power to compare each test schedule separately with the control will be higher. The calculations allow for up to 10% loss to follow-up / unevaluable.

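### Section 17.2 does not name the local-relapse risk group used to stratify randomisation in any analysis of local recurrence; naming it is a free, low-priority improvement

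*Protocol*

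**What the plan says.** - **Design.** Section 7.2: "Randomisation will be stratified by centre and risk group". Section 2 gives the purpose, "Stratification by treatment centre and by local relapse risk will ensure balanced trial groups", and the definition: "high risk defined as patient age <50 and/or grade 3 tumour; low risk defined as age ≥50 and grade 1 or 2 tumour". The factor was therefore chosen for its link to local relapse, which section 5.1 makes the primary endpoint.
- **Main comparison.** Section 17.2 says that Kaplan-Meier and Cox methods "will be used to compare rates of local recurrence between allocated treatments for all randomised patients". It names no covariate or stratum there.
- **Adjusted analyses.** Later in 17.2: "Analyses of local tumour recurrence and of normal tissue effects adjusting for adjuvant therapy (chemotherapy, hormonal therapy) will be performed". The next sentence adds breast size and surgical deficit, for normal tissue effects only.
- **Per-protocol set.** Sections 9.1 and 17.2 add an analysis of compliant patients if non-compliance in the test groups is high. Intention to treat remains the basis.
- **Risk group as an analysis factor.** It is not named as one anywhere in the protocol, and nothing says that it will be left out.

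**The concern.** A factor that was balanced by design because it predicts the primary endpoint would normally be carried into the analysis of that endpoint. Section 17.2 does choose a covariate for local recurrence, but not this one. Three effects could follow.

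1. On the absolute scale, where the 1.6-point margin is set, an analysis that ignores the stratifier overstates the standard error.
2. In a Cox model, leaving out a prognostic factor pulls the hazard ratio slightly towards 1. If a test schedule is worse, that is the lenient direction for non-inferiority.
3. In a compliant-only set, patients are removed after allocation is known, so stratified randomisation no longer guarantees risk balance. If high-risk patients leave a test group more often, that group's relapse rate looks better than it is.

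The question is how large each effect can be.

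**Working it through.** **Inputs from the protocol (7.2, 17.3.1).** 4,000 patients, 1:1:1; control 5-year rate p = 2%; margin 1.6 points; one-sided alpha 0.025; power 80%; 10% loss.

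**Assumed, because the protocol gives neither.** High-risk share q = 20-50%; high:low ratio of 5-year relapse rates r = 1.5-5. Then pL = p/(1 − q + qr) and pH = r·pL.

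**1. The plan's own sample size**
- n = (1.960 + 0.842)² × 2 × 0.02 × 0.98 / 0.016² = 1,202 per group.
- 1,202/0.9 = 1,336 per group; × 3 = 4,008, against 4,000 stated. It reproduces on the rate-difference scale.
- With 1,200 evaluable per group, SE = √(2 × 0.0196/1,200) = 0.005715, and power = Φ(0.016/0.005715 − 1.960) = 79.9%.

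**2. Intention to treat, absolute difference**

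Share of variance removed by stratifying = q(1 − q)(pH − pL)² / [p(1 − p)].

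| q | r | pL | pH | Share | SE | Power | Equivalent N |
|---|---|---|---|---|---|---|---|
| 20% | 1.5 | 1.82% | 2.73% | 0.07% | 0.005714 | 80.0% | 3,997 |
| 40% | 3 | 1.11% | 3.33% | 0.60% | 0.005698 | 80.2% | 3,976 |
| 20% | 5 | 1.11% | 5.56% | 1.61% | 0.005669 | 80.6% | 3,936 |

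The last row is the largest gain on the grid. The SE falls by 0.03-0.8%.

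**3. Intention to treat, Cox model**
- *Precision.* In simulations (1,200 per arm, balanced on risk group, 3,000 runs per scenario), the mean model SE of the log hazard ratio was 0.2939 unadjusted and 0.2939 stratified in one scenario, and 0.2598 and 0.2598 in another. The empirical SD was not smaller after stratifying (0.3012 unadjusted, 0.3027 stratified). There is no gain in precision.
- *Attenuation.* The margin corresponds to a hazard ratio of ln(0.964)/ln(0.98) = 1.81. With 40% high risk, a conditional hazard ratio of 1.81 appears unadjusted at 5 years as 1.808, 1.806 or 1.803 for r = 2, 3 or 4. The largest of these shifts is ln(1.81/1.803) = 0.004, or 0.004/0.2939 = 1.4% of one standard error.
- *Extreme corner (q = 20%, r = 5).* Test-group survival is 0.8 × 0.98889^1.81 + 0.2 × 0.94444^1.81 = 0.9643. The unadjusted ratio is ln(0.9643)/ln(0.98) = 1.80, a shift of about 0.007, still only 2% of a standard error.

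**4. Per-protocol set**

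Shift in the 5-year difference = risk imbalance between arms × (pH − pL).
- Smallest: 2 points, q = 50%, r = 1.5: 0.02 × (2.4 − 1.6) = 0.016 points.
- Largest: 5 points, q = 20%, r = 5: 0.05 × (5.56 − 1.11) = 0.22 points.
- The range is about 0.02-0.2 points, or 1% to 14% of the 1.6-point margin.
- Example with q = 40%, r = 3: remove 5% of a test group, all high risk. Its rate becomes (0.35 × 3.33 + 0.60 × 1.11)/0.95 = 1.93% instead of 2.00%. That is a spurious benefit of 0.07 points, from a high-risk share of 0.35/0.95 = 36.8% instead of 40%.

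**The case against.** The strongest objection is that strata and covariates are routinely fixed in the SAP, which is not at hand, and that silence about risk group is not a decision to omit it. This largely stands: the text contains no error and no contradiction, and the SAP may already stratify. It does not dispose of the point, because 17.2 does choose a covariate for recurrence and that choice passes over the design factor.

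Four stronger readings are tempting, and the documents do not support them.

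- *The primary comparison is adjusted for adjuvant therapy.* The main comparison is stated without covariates. The adjuvant-therapy sentence describes additional analyses, covering recurrence and normal tissue effects together.
- *Standard errors are too large throughout.* This is true only for the absolute difference, where it is under 1% and makes the non-inferiority test conservative. It is not true of the Cox model.
- *A non-inferiority conclusion is at risk.* No calculation here shows that. The attenuation is a small fraction of a standard error.
- *Stratifying would protect the per-protocol analysis.* It would remove only the part of any selection that runs through this one binary factor.

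It is also fair to say that the per-protocol analysis is conditional and supplementary, and that no passage suggests that non-compliance will concentrate in high-risk patients. The worked example is an illustration and not a forecast.

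**Conclusion.** The point holds as a minor one. The analysis of the primary endpoint, as written, does not name the relapse-risk stratifier, and the only covariate named for recurrence is a different one, in further analyses. Under intention to treat the consequence is close to nil on either scale. The practical value lies in the per-protocol analysis, where a modest imbalance could move the 5-year difference by up to roughly a seventh of the margin in the least favourable corner and usually by much less.

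All sizes rest on assumed risk shares and relapse ratios. The per-protocol figure also rests on an assumed imbalance of 2-5 points.

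**What to change.** In section 17.2, state that:

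- the Cox comparison of each test group with control is stratified by the randomisation risk group;
- the absolute 5-year difference is a stratum-weighted Kaplan-Meier difference;
- both apply to the intention-to-treat analysis and to any per-protocol analysis;
- risk group is kept in the model that adjusts for adjuvant therapy.

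Risk group alone is enough as a stratum. At 2% of 1,200 there are about 24 control relapses by 5 years. Over the roughly 20 centres expected in Appendix 3, that is 24/20 = 1.2 per centre, too few for centre strata to be useful.

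The cost is a sentence or two of wording. Risk group must already be known to allocate each patient, so no data, visits, patients or power are lost. If the SAP already says this, the protocol only needs to be aligned with it.
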